### 14.2. Sample Size Justification

There will be one testing site: VRC [REDACTED] A total of approximately 32 eligible subjects will be enrolled into the study at this site. At least 24 subjects will complete this study. There have been no prior historical studies to evaluate the number of modifications needed in the Test article. As such, the sample size calculation was not based on any power analysis with regard to the primary endpoint.

Using the POWER procedure in SAS 9.4, below is the summary of sample size required based on the different assumptions of the true percentage of subjects with at most one modification.

- Percentage of subjects with at most one modification

True Percentage (%)	# of subjects needed	Power
70	56	0.913

[REDACTED] (5)

75	35	0.924
80	23	0.928

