#### **Other Observation(s)**

### **2.3. Hypotheses**

#### **Primary Hypotheses**

The maximum number of modification required by the ECP to optimize vision will not exceed one modification in more than 50% of the subjects.

Secondary Hypotheses  
Not Applicable

Other Hypotheses  
Not Applicable

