#### **14.4. Level of Statistical Significance**

All planned analysis for this study will be conducted with an overall type I error rate of 5%.

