#### **14.5. Primary Analysis**

Primary efficacy analysis:

Due to the potential low incidence rates of unacceptable lens fitting, summary statistics will be firstly used to evaluate the percentage of the subjects with at most one optimization per-protocol population.

Due to the potential low incidence rates of unacceptable lens fitting, summary statistics will be firstly used to evaluate the percentage of the subjects with at most one optimization per-protocol population.

If applicable, a generalized linear mixed model with a binary distribution and logit link function will be applied to the number of modifications (1=at most one modification; 0 = more than one modification). Age, gender and subjects' add power will be included in the model as fixed effects when appropriate. ECP and subject will be included as random effect.

The proportion of subjects with at most one optimization will be calculated with 95% confidence interval. If the lower limit of the confidence interval is greater than 50%, the statistical superiority will be concluded.

[REDACTED] (5)

If the incidence rate is too low or there are problems with the convergence of the above model, Agresti methods or Fisher's exact test for binomial proportion will be used to evaluate the confidence intervals of the corresponding endpoints.

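### The power figures in 14.2 fit a one-sided 5% rule, but no section states the sides; if the 95% interval in 14.5 is two-sided in the usual sense, they are 5 to 9 points too high

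*Combined protocol and SAP*

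**What the plan says.** Section 14.2 says that no earlier study informs the number of modifications, and continues: "As such, the sample size calculation was not based on any power analysis with regard to the primary endpoint". It then gives a table from the SAS POWER procedure, introduced by "below is the summary of sample size required based on the different assumptions of the true percentage of subjects with at most one modification". Its three rows are these:

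| Assumed rate (%) | Size | Power |
|---|---|---|
| 70 | 56 | 0.913 |
| 75 | 35 | 0.924 |
| 80 | 23 | 0.928 |

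The test, alpha, null value and number of sides behind the table are not given. On size, the section plans for about 32 enrolled and says "At least 24 subjects will complete this study".

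The primary hypothesis in 2.3 is directional: "The maximum number of modification required by the ECP to optimize vision will not exceed one modification in more than 50% of the subjects". Section 14.4 sets an overall type I error of 5% without sides.

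The decision rule is in 14.5. The estimate comes first: "The proportion of subjects with at most one optimization will be calculated with 95% confidence interval". Success is then defined in these terms: "If the lower limit of the confidence interval is greater than 50%, the statistical superiority will be concluded". That section starts with summary statistics and, where applicable, a logistic mixed model with ECP and subject as random effects. A simple binomial interval is the fallback, by one of two named routes, the second being an exact test: "If the incidence rate is too low or there are problems with the convergence of the above model, Agresti methods".

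**The concern.** A power figure should describe the rule by which the study will be judged. A lower-limit rule spends up to 5% in the relevant direction if the 95% bound is one-sided, and nominally 2.5% if the interval is two-sided. The plan does not say which applies. An analyst who follows 14.5 literally would compute a two-sided interval. If the table was built on a one-sided 5% rule, the only power figures in the plan then belong to a more lenient criterion than the one applied.

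Two things are at stake: whether the printed powers are right for the stated rule, and whether the pass mark is fixed before the data are seen. In some cases the unwritten choice decides whether the same count is a success or a failure.

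**Working it through.** **Inputs.** Null value 50% (2.3 and 14.5); error rate 5% (14.4); true percentages, sizes and powers (14.2); at least 24 completers (14.2). Subjects are taken as independent and the interval as simple binomial.

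**Step 1: reproduce the table.** Let c be the smallest count with P(X ≥ c | n, 0.5) ≤ 0.05. Power is P(X ≥ c | n, p) at the true percentage p.

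| n | p | c | Null tail | Power | Printed |
|---|---|---|---|---|---|
| 56 | 0.70 | 35 | 0.0407 | 0.9126 | 0.913 |
| 35 | 0.75 | 23 | 0.0448 | 0.9244 | 0.924 |
| 23 | 0.80 | 16 | 0.0466 | 0.92849 | 0.928 |

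All three rows match to the printed decimal. The one-sided normal approximation with null variance gives 0.929, 0.935 and 0.938, which does not match; nor does the exact test at two-sided 5%. One-sided 95% Clopper-Pearson, Wilson, Agresti-Coull and Wald bounds all give the same cut-offs of 35, 23 and 16. The table therefore points to the sides, but not to the interval method.

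**Step 2: apply a two-sided 95% interval at those cut-offs.** Lower limits:

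| Count | Clopper-Pearson | Wilson | Agresti-Coull | Wald |
|---|---|---|---|---|
| 35/56 | 0.4855 | 0.4941 | 0.4938 | 0.4982 |
| 23/35 | 0.4779 | 0.4915 | 0.4908 | 0.4999 |
| 16/23 | 0.4708 | 0.4913 | 0.4894 | 0.5076 |

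Worked example, Agresti-Coull at 16/23: z² = 3.8415, so the adjusted size is 26.8415 and the adjusted proportion is (16 + 1.9207)/26.8415 = 0.66765. The limit is 0.66765 − 1.96 × √(0.66765 × 0.33235/26.8415) = 0.66765 − 0.17820 = 0.48945, below 50%. Wald at the same count: 0.69565 − 1.96 × √(0.69565 × 0.30435/23) = 0.69565 − 0.18805 = 0.5076, above 50%.

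**Step 3: cut-offs and power on the two-sided reading.** Clopper-Pearson, Wilson and Agresti-Coull agree:

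| n | Needed | Null tail | Power | Printed minus this |
|---|---|---|---|---|
| 56 | 36 | 0.0220 | 0.859 | 0.913 − 0.859 = 0.054 |
| 35 | 24 | 0.0205 | 0.858 | 0.924 − 0.858 = 0.066 |
| 23 | 17 | 0.0173 | 0.840 | 0.928 − 0.840 = 0.088 |

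A two-sided Wald interval, which 14.5 does not name, gives 36, 24 and 16. It leaves the last row at 0.928.

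**Step 4: the planned 24 completers.**

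| Method | One-sided | Two-sided |
|---|---|---|
| Wilson, Agresti-Coull | 17 | 17 |
| Clopper-Pearson | 17 | 18 |
| Wald | 16 | 17 |

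| Cut-off at n = 24 | Null tail | Power at 70% | 75% | 80% |
|---|---|---|---|---|
| 17 | 0.032 | 0.565 | 0.766 | 0.911 |
| 18 | 0.011 | 0.389 | 0.607 | 0.811 |

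The Wald cut-off of 16 has null tail 0.076 and power 0.964 at 80%.

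The target is a minimum, so other sizes can occur. At n = 28, for example, Clopper-Pearson, Wilson and Agresti-Coull all move from 19 to 20, and power at 80% goes from 0.961 to 0.910.

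**The case against.** The strongest reply is that the plan fits a one-sided reading throughout. The hypothesis is directional, only the lower limit is used, the 5% in 14.4 is what a one-sided 95% bound spends, and the table matches that rule. On this view nothing is miscalculated and one word is missing. That stands as a possible intention, so a reader who infers that the 14.2 table is simply wrong goes further than the documents allow. It does not settle the matter. A directional claim can also be tested with the lower limit of a two-sided interval, and an unqualified 95% interval is ordinarily read that way.

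A second reply is that nothing in the design rests on the table. This also stands. Section 14.2 says the size was not power-based, and the rows for 56 and 35 subjects lie beyond the planned enrolment of about 32. A reader might infer that the trial is too small or needs more subjects; this point does not support that.

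Third, at exactly 24 completers the sides make no difference with Agresti-Coull, a fallback that 14.5 names in general terms, or with Wilson. That is correct, but it does not extend to the exact fallback.

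Fourth, the mixed model precedes the simple interval in 14.5, and these figures do not cover it. That is a real limit on the numbers. The model's interval would still need its sides stated.

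**Conclusion.** The point holds conditionally. The printed powers belong to a one-sided 5% rule, and the plan never says that its success rule is one-sided. If the interval in 14.5 is two-sided by Clopper-Pearson, Wilson or Agresti-Coull, the printed powers are 5.4, 6.6 and 8.8 points too high. With Wald, only the first two rows are affected. If a one-sided bound is meant, the table is correct and 14.5 is incomplete.

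The practical weight is moderate. Only the row for 23 subjects is near the planned size. At 24 the effect ranges from none (Wilson, Agresti-Coull) to 10 points of power at a true 80% (Clopper-Pearson, 0.911 to 0.811). All of this assumes independent subjects and a simple binomial interval, so any correlation among subjects fitted by the same ECP is left out.

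**What to change.** State the sides and name one interval method in 14.4 and 14.5, before any data are seen. Then choose one of two routes:

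- **Two-sided 95% intended:** restate the powers in 14.2 under the named method. They are 0.859, 0.858 and 0.840 for Clopper-Pearson, Wilson or Agresti-Coull.
- **One-sided 5% intended:** keep the table, say in 14.2 that it is an exact binomial test of 50% at one-sided 5%, and define the rule in 14.5 as a one-sided 95% lower bound.

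On either route, add a row for 24 subjects under the named method, and note that the figures are simple binomial and do not cover the mixed model.

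The cost is wording and one table, with no extra subjects. The first route shows less favourable power. The second openly accepts a one-sided 5% error, with an actual rate of 0.032 at 24 subjects under a cut-off of 17.

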## SYNOPSIS

Protocol Title	Evaluation of the JJVC Investigational Toric Multifocal Contact Lens Fitting Guide Phase II
Sponsor	JJVC, [name]
Clinical Phase	Phase 2
Trial Registration	This study will be registered on ClinicalTrials.gov by the Sponsor
Test Article(s)	Investigational Products: etafilcon A Toric Multifocal Contact Lens Marketed Products: 1-Day Acuvue® Moist Brand Multifocal Contact Lens
Wear and Replacement Schedules	Wear Schedule: Daily Wear Replacement Schedule: None- Non-dispensing study
Objectives	The primary objective of this study is an evaluation of the JJVC Investigational Toric Multifocal and 1-Day Acuvue® Moist Brand Multifocal Contact Lens fitting guides by Eye Care Providers (ECPs).

[REDACTED] (5)

Study Endpoints	
Primary endpoint: The maximum number of lens modifications for both eyes required by the ECP to optimize the lenses for vision.
 
Secondary endpoint:
 
 
1. Subjective feedback from the ECP on the fitting guide process (i.e. intuitive nature of the fitting steps, adequate amount of information provided by the fitting guide, strengths and weaknesses, etc.)
 
2. Subjective feedback from the ECP regarding the layout of the fitting guide.
 
3. Surveys of the subjects experience.
 

Study Design	
This study is a single arm, non-randomized, open label, non-dispensing clinical trial. The key assessments for this study will be the number of fitting modifications and ECP feedback throughout the fit process while using the Fit Guide. Each ECP will fit at least 3 subjects and no more than 4.
 
See the flow chart at the end of the synopsis table for the schematic of the study visits and procedures of main observations.

Sample Size	
A total of approximately 32 subjects will be enrolled into the study. Approximately 24 are targeted to complete.

Study Duration	
The study duration is anticipated to be approximately 1 week.

Anticipated Study Population	
Healthy male and female volunteers with presbyopia will be screened as per criteria outlined below.

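### The 0.928 power in section 14.2 rests on independent subjects and a one-sided 5% test; under the section 14.5 exact rule, 24 completers give about 0.76–0.81, and the fallback interval ignores ECP

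*Combined protocol and SAP*

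**What the plan says.** - **Section 14.2.** About 32 subjects are enrolled and at least 24 complete. The section states that "the sample size calculation was not based on any power analysis with regard to the primary endpoint", and then gives PROC POWER results, introduced with "below is the summary of sample size required based on the different assumptions of the true percentage of subjects with at most one modification": 70% true success, 56 subjects, power 0.913; 75%, 35, 0.924; 80%, 23, 0.928. It names no test, significance level or sidedness, and makes no allowance for ECP.
- **Section 14.4.** "All planned analysis for this study will be conducted with an overall type I error rate of 5"%. Sidedness is not stated.
- **Section 14.5, decision rule.** A 95% interval is calculated and "If the lower limit of the confidence interval is greater than 50%, the statistical superiority will be concluded".
- **Section 14.5, model.** Where applicable, a logit mixed model is fitted, in which "ECP and subject will be included as random effect".
- **Section 14.5, fallback.** If incidence is too low or the model does not converge, Agresti methods or an "exact test for binomial proportion will be used to evaluate the confidence intervals of the corresponding endpoints". Neither is preferred and neither carries an ECP term.
- **Synopsis, Study Design.** "Each ECP will fit at least 3 subjects and no more than 4". Sections 4.1 and 4.3 give only the maximum of 4.
- **Section 7.2, steps 1.23–1.24.** The ECP decides whether a lens change is needed.

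The documents state neither the number of ECPs nor an ICC.

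**The concern.** The outcome is whether a subject needed at most one modification, and the ECP makes that decision. Outcomes within one ECP may therefore be alike, which is what the random effect in 14.5 allows for. The power table and the fallback interval both omit it. The table also appears to use a different significance level from the decision rule.

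Two things are at stake. A reader will take 0.928 as this study's power, because the 80% row (23 subjects) is the only one near the 24 planned completers. And if the fallback decides the primary conclusion, its false-success rate may differ from what the plan implies.

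The fallback is a realistic path. The synopsis defines the endpoint as a maximum over both eyes, so there is one binary outcome per subject. A subject random effect is then not separately identifiable, and the model would also carry ECP and three covariates on about 24 outcomes.

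**Working it through.** **Inputs.** Null value 50% and 95% limit (14.5); table rows and 24 completers (14.2); 3–4 subjects per ECP (Synopsis). This implies 24/4 = 6 to 24/3 = 8 ECPs among completers. That is derived, not stated; if all 32 enrolled were fitted, it would be at least 32/4 = 8. The ICC is assumed at 0, 0.05, 0.10 and 0.20.

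**Step 1: reproduce the table.** Let X be binomial(n, p). Take the smallest r with P(X ≥ r | 0.5) ≤ α; power is P(X ≥ r | p).

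| n, true p | r at one-sided 5% | Power | Stated | r at one-sided 2.5% (95% limit) | Power |
|---|---|---|---|---|---|
| 56, 0.70 | 35 | 0.9126 | 0.913 | 36 | 0.859 |
| 35, 0.75 | 23 | 0.9244 | 0.924 | 24 | 0.858 |
| 23, 0.80 | 16 | 0.9285 | 0.928 | 17 | 0.840 |

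One-sided 5% with independent subjects matches every row. Two-sided 5% does not, nor does any normal approximation tried.

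**Step 2: cut-offs at 24 completers.**
- Clopper-Pearson lower limit: 0.489 at 17/24 and 0.533 at 18/24, so success needs 18.
- Agresti-Coull: ñ = 24 + 1.96² = 27.84; p̃ = (17 + 1.92)/27.84 = 0.680; lower limit = 0.680 − 1.96 × √(0.680 × 0.320/27.84) = 0.506. So 17 suffices.

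**Step 3: add clustering.** Each ECP's success probability is drawn from Beta(ps, (1 − p)s) with s = 1/ICC − 1. The count per ECP is then beta-binomial, and counts are convolved exactly over 8 ECPs of 3 or 6 ECPs of 4. Ranges cover the two layouts.

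| ICC | Power at 80%, ≥18/24 | One-sided error, exact (≥18) | One-sided error, Agresti-Coull (≥17) |
|---|---|---|---|
| 0 | 0.811 | 1.1% | 3.2% |
| 0.05 | 0.797–0.801 | 1.5–1.7% | 3.9–4.2% |
| 0.10 | 0.784–0.792 | 1.9–2.3% | 4.6–5.3% |
| 0.20 | 0.764–0.777 | 2.8–3.7% | 6.0–7.4% |

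The exact rule reaches 2.5% at ICC 0.113 (4 per ECP) or 0.170 (3 per ECP).

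**Step 4: split the gap at 80% true success.**
- 5% to 2.5% one-sided at n = 23: 0.928 − 0.840 = 0.088.
- Discrete cut-off, n = 23 to n = 24: 0.840 − 0.811 = 0.029.
- Clustering at the fixed cut-off of 18: 0.010–0.015 at ICC 0.05, 0.019–0.027 at 0.10, 0.034–0.047 at 0.20.

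**The case against.** - **The table did not set the sample size.** Section 14.2 says so, and correcting it changes neither enrolment nor conduct. That stands and limits the weight of the point. The figure is still printed as power for this endpoint and does not match the rule in 14.5.
- **The main model already includes ECP.** That also stands. The error-rate point concerns the fallback only. A reader might infer that the primary analysis as a whole is anti-conservative; the documents do not support that.
- **Clustering is not the main cause.** A reader might attribute the whole fall from 0.928 to clustering. Step 4 shows that about 0.117 of it (0.088 + 0.029) arises with independent subjects.
- **Effective sample size suggests a larger loss.** Dividing 24 by 1 + (m − 1) × ICC, with m subjects per ECP, and rounding gives exact powers such as 0.716 at n = 18 and 0.648 at n = 15. Binomial power is saw-toothed at these sizes: n = 17 gives 0.758, higher than n = 18. These values are rounding artefacts, and the direct calculation in Step 3 replaces them.
- **False success is not inflated in general.** The exact fallback has slack (1.1% at ICC 0). Agresti-Coull exceeds 2.5% before any clustering, so clustering worsens that excess but does not cause it.
- **The limit might be meant as a one-sided 95% bound.** Then 17/24 would suffice (null tail probability 3.2%, below 5%), power with independent subjects would be P(X ≥ 17 | 24, 0.8) = 0.911, and little beyond clustering would remain. Section 14.5 does not say this; an unqualified 95% interval is ordinarily two-sided.

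**Conclusion.** The point holds in limited form. The section 14.2 table describes independent subjects tested at one-sided 5%, and section 14.5 describes neither. At 80% true success and 24 completers, the exact 95% interval gives power 0.81 with independent subjects and 0.76–0.80 over ICC 0.05–0.20, against the printed 0.928. Sidedness and discreteness account for most of the difference; clustering adds about 1–5 points.

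The unadjusted fallback is a problem mainly because Agresti is allowed, with 3.2% one-sided error at ICC 0 and up to 7.4% at ICC 0.20. The exact option breaches 2.5% only above an ICC of about 0.11–0.17.

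This rests on an assumed ICC range, a two-sided 95% interval, Agresti methods meaning Agresti-Coull, the exact option meaning Clopper-Pearson, and equal ECP groups of 3 or 4. Power of the mixed model itself was not computed.

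**What to change.** **Section 14.2.** State the test and sidedness behind the table. Restate power at 24 completers for the 95% interval rule at ICC 0, 0.05, 0.10 and 0.20, labelled as assumed values.

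**Section 14.5.** Name the exact (Clopper-Pearson) interval, not Agresti, as the single fallback. Report an ECP-cluster-adjusted interval over the same ICC values as a sensitivity analysis, for example Clopper-Pearson on 24/[1 + (m − 1) × ICC] subjects.

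The adjusted interval should not become the fallback itself. It needs an ICC that the plan lacks. It would also raise the cut-off to 19/24 at ICC 0.10 with 4 per ECP, and at ICC 0.20 with either group size, leaving power of about 0.64–0.65.

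**Cost.** SAP wording and a short calculation, with no change to enrolment or procedures. Stated power falls to about 0.76–0.81 from 0.928. The fallback needs 18/24 rather than 17/24; with independent subjects and 80% true success that lowers power from 0.911 to 0.811.

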#### **14.3. Analysis Populations**

Not Applicable

**Safety Population:**

All subjects who were administered any Test article excluding subjects who drop out prior to administering any Test article. At least one observation should be recorded.

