### **8.2. Withdrawal/Discontinuation from the Study**

A subject will be withdrawn from the study for any of the following reasons:

- Subject death during the study period
- Subject withdrawal of consent
- Subject not compliant to protocol
- Subject lost to follow-up
- Subject no longer meets eligibility criteria (e.g. the subject becomes pregnant)
- Subject develops significant or serious adverse events causing discontinuation of study lens wear
- Subjects who have experienced a Corneal infiltrative Event (CIE)
- Investigator's clinical judgment regarding the subject safety reasons (that it is in the best interest of the subject to stop treatment)
- Subject not compliant with study lens wear schedule
- Subject not successfully dispensed due to lack of efficacy and safety including poor vision, poor comfort or unacceptable fit

For discontinued subjects, the Investigator will:

- Complete the current visit (scheduled or unscheduled)
- Complete the Final Evaluation, indicating the reason that the subject was discontinued from the study
- Record the spherocylindrical refraction with best corrected distance visual acuity
- Collect used Test article(s) (worn or brought to the visit) from the subject and discard them, unless otherwise stated in Section 7.2
- Collect all unused Test article(s) from the subject

An additional subject may be enrolled if a subject discontinues from the study prematurely.

In cases where a subject is lost to follow-up, every possible effort must be made to contact the subject and determine the reason for discontinuation/withdrawal. The measures taken to follow up must be documented including two written attempts and a certified letter (or equivalent) as the final attempt.

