## 14. STATISTICAL METHODS

### 14.1. General Considerations

All data summaries and statistical analyses will be performed using the SAS software Version 9.4 (SAS Institute, Cary, NC). Throughout the analysis of data, the results for each subject/eye will be used when available for summarization and statistical analysis. Unscheduled visits will be summarized separately and will be excluded from the statistical analysis.

Summary tables (Descriptive statistics and/or frequency tables) will be provided for all baseline variables, efficacy variables and safety variables as appropriate. Continuous variables will be summarized with descriptive statistics (n, mean, standard deviation (SD), median, minimum and maximum). Frequency count and percentage of subjects or eyes within each category will be provided for categorical data.

Summaries will be presented by study lens type and will be performed separately by completion status. All analyses will be conducted on per-protocol population (see section 14.3).

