**Per-Protocol Population:**

All subjects who have successfully completed all visits and did not substantially deviate from the protocol as determined by the trial cohort review committee prior to database hard lock (Per-Protocol Population). Justification of excluding subjects with protocol deviations in the per-protocol population set will be documented in a memo to file.

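### Section 14.1 promises safety tables but puts all analyses on per-protocol completers, and the Safety Population defined in 14.3 is assigned to no table

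*Combined protocol and SAP*

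**What the plan says.** Section 14.1 promises safety tables: "Summary tables (Descriptive statistics and/or frequency tables) will be provided for all baseline variables, efficacy variables and safety variables as appropriate". It names no population there. Two consecutive sentences later in the section then point in different directions. The first is "Summaries will be presented by study lens type and will be performed separately by completion status". The second is "All analyses will be conducted on per-protocol population", with a cross-reference to 14.3. Neither mentions an exception for safety variables.

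Section 14.3 is marked not applicable directly under its heading, yet goes on to define three sets:

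- **Safety:** "All subjects who were administered any Test article excluding subjects who drop out prior to administering any Test article", with at least one recorded observation.
- **Per-protocol:** "All subjects who have successfully completed all visits and did not substantially deviate from the protocol", as judged by a review committee before lock.
- **ITT:** defined through randomization, which sections 4.1 and 5.3 say this study does not have.

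No table or analysis in section 14 is given to the Safety Population, and the section has no part on safety analysis.

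Section 8.1 does not count as a completer anyone withdrawn under section 8.2. The withdrawal reasons in 8.2 include "Subject develops significant or serious adverse events causing discontinuation of study lens wear", a corneal infiltrative event, the investigator's judgment on safety, and unacceptable fit.

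**The concern.** A safety table should count everyone who was exposed to the lens. The per-protocol set is selected partly on safety outcomes, because an event that ends participation also removes the subject from the set. If the safety tables are built on it, the events most worth reporting are the ones least able to appear, and the table leans towards showing none. The protocol already contains the right population for these tables but never connects it to them. As the text stands, a programmer cannot tell which subjects belong in the safety summaries of an investigational lens.

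**Working it through.** **1. The plan's own figures.** The only computed figures are in the sample-size table of 14.2. A one-sided exact binomial test of 50% at 0.05 reproduces them:

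| True % | n | Reject if at least | Actual alpha | Power | Stated power |
|---|---|---|---|---|---|
| 70 | 56 | 35 | 0.0407 | 0.913 | 0.913 |
| 75 | 35 | 23 | 0.0448 | 0.924 | 0.924 |
| 80 | 23 | 16 | 0.0466 | 0.928 | 0.928 |

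None of these depends on the population used for safety, so the point leaves them untouched.

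**2. The chain of definitions.** All analyses are per-protocol (14.1). Per-protocol requires completion (14.3). Completion excludes withdrawal under 8.2 (8.1). Section 8.2 includes significant or serious adverse events that stop lens wear. Followed literally, a subject withdrawn for such an event is in no analysed set.

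**3. Whether exposed subjects can be lost this way.** Lenses are inserted at step 1.19 of section 7.2. An unacceptable toric fit at step 1.20 sends the subject to biomicroscopy and the Final Evaluation. An unacceptable lens fit at step 1.21 leads to discontinuation with a slit-lamp examination. Both come after insertion, so exposed non-completers with slit-lamp data are foreseen by the visit itself. In contrast, subjects who fail at steps 1.6, 1.15 or 1.16 stop before insertion and belong in neither population.

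**4. Upper bound on the number affected.** Inputs from 14.2: about 32 enrolled, at least 24 completing.

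- Non-completers: at most 32 − 24 = 8, and 8/32 = 25%.
- Let E be the number of these who were exposed. Then E lies between 0 and 8; the documents do not give it.
- Completers removed for substantial deviations would come on top; their number is not given either.

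**5. Effect on a reported rate.** Assume 24 per-protocol subjects and k subjects who stop because of an event, with k no larger than E. These k subjects contribute 0/24 to a per-protocol table and k/(24 + E) to a Safety Population table. The values of k are illustrations, not forecasts.

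| k | Per-protocol | Safety Population, E = k | Safety Population, E = 8 (95% exact interval) |
|---|---|---|---|
| 1 | 0/24 = 0% | 1/25 = 4.0% | 1/32 = 3.1% (0.08% to 16.2%) |
| 2 | 0/24 = 0% | 2/26 = 7.7% | 2/32 = 6.3% (0.8% to 20.8%) |

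The 95% exact interval for 0/24 has upper limit 1 − 0.025^(1/24) = 14.2%.

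**6. Events unrelated to dropout.** The chance of seeing at least one event is 1 − (1 − r)^n. At r = 1% it is 27.5% with n = 32 and 21.4% with n = 24. At r = 5% it is 80.6% and 70.8%. For events of this kind the loss is moderate. For events that themselves cause discontinuation, the chance of appearing in a per-protocol table is zero.

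**The case against.** The strongest reply is that 14.1 treats summaries and analyses as different things. Its opening sentence names both, and "Unscheduled visits will be summarized separately and will be excluded from the statistical analysis" uses them as separate terms. Safety variables are placed under summary tables, and summaries are to be split by completion status, which has meaning only if non-completers are summarized. On that view the per-protocol sentence covers inference alone.

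This stands to the extent that a reader might infer from 14.1 that safety events are certain to be excluded by construction, and the documents do not support that. No sentence says the safety tables are per-protocol only, and the completion-status sentence points the other way. But the reply does not settle the matter. Section 14.5 places summary statistics under its primary efficacy analysis, so the plan does not keep the two terms apart. And a split by completion status gives two tables with no all-exposed total, where the non-completer table may mix subjects who wore a lens with subjects who never did.

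Three further replies are fair:

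- **Not every event removes a subject.** Section 13.3 leaves continuation to the investigator's judgment, and an event found at exit biomicroscopy (step 1.26) need not end participation. Such a subject can be a completer. Unacceptable fit is also not in itself an adverse event.
- **Nothing is lost from the record.** A reader might infer that events disappear from the study. Section 13.3 requires all of them to be documented, and 13.4 sets deadlines for reporting them to the sponsor.
- **Safety is not an objective, endpoint or hypothesis in section 2**, and section 4.1 gives only about 30 to 90 minutes of wear, so few events are likely.

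These limit the weight of the point. They do not tell the programmer whom to tabulate.

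**Conclusion.** The point holds as a contradiction in 14.1 together with an unused Safety Population. Under the literal reading of the per-protocol sentence, exposed subjects who are discontinued after insertion are left out of the safety tables. Under the most favourable reading, they appear in a separate table and no all-exposed rate is planned.

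The size is at most 8 of about 32 subjects (25%) through non-completion. A reader might take 25% as the share of exposed subjects omitted. The documents do not support that, because eligibility failures before step 1.19 may be among the 8 and 24 is a minimum for completers. The rates shown for one or two events assume that such events occur among exposed non-completers and that no completer is removed for deviations; the protocol gives no expected event rate.

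The defect lies in the reported summaries, not in data capture, and neither the primary result nor the sample size is affected. It should be fixed, but it does not put the trial's main conclusion at risk.

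**What to change.** Change 14.1 in two places, before database lock:

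1. Limit the per-protocol sentence to the primary efficacy analysis. Per-protocol then remains the stated population for the primary endpoint, and no new efficacy population has to be defined.
2. State that adverse event, biomicroscopy and visual acuity summaries use the Safety Population, meaning all subjects in whom a study lens was inserted. Show any split by completion status in addition to the all-exposed total, not in its place.

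In 14.3, delete the not-applicable line above the definitions so that the cross-reference from 14.1 leads to populations that are in force.

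The cost is a few lines of text. No new data are needed: adverse events have their own eCRF (13.3), slit-lamp findings are taken at exit (step 1.26) or at discontinuation (steps 1.20 and 1.21), and acuity with refraction is recorded at the Final Evaluation. Sample size, power and the primary analysis stay as they are.
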